Phase II Trial of Neutron Radiotherapy with Concurrent Checkpoint Inhibitor Immunotherapy (pembrolizumab) in Patients with Advanced Urothelial Carcinoma

Principal Investigator: [name]
Associate Professor
Department of Radiation Oncology
University of Washington Medical Center
[name]
[name]
[contact]
[contact]
Email: [contact]

Co-Investigators: [name]
[name] PhD
[name]
[name], PhD
[name]
[name]
[name], PhD
[name] [name]
[name]
[name]
[name]

Version: 01/08/2019

Study Summary

Title	Phase II Trial of Neutron Radiotherapy with Concurrent Checkpoint Inhibitor Immunotherapy (pembrolizumab) in Patients with Advanced Urothelial Carcinoma
Short Title	Neutron + Pembrolizumab in Advanced Urothelial Cancers
Protocol Number	CC 9940
Phase	II
Methodology	1 Arm Open-Label
Study Duration	2 yrs
Study Center(s)	University of Washington Medical Center
Objectives	To primary objective is to assess whether neutron radiation (with high relative biological effectiveness relative to standard photon radiation) to a single focus of disease in patients with advanced urothelial carcinoma, can improve the overall response rate to standard of care checkpoint inhibitor immunotherapy (pembrolizumab). The primary endpoint is the overall response rate per iRECIST. Secondary objectives are to evaluate toxicity, immune-related clinical responses and immune pharmacodynamic changes, progression-free survival, and overall survival.
Number of Subjects	20 evaluable subjects
Diagnosis and Main Inclusion Criteria	Patients diagnosed with advanced urothelial carcinoma, about to start checkpoint inhibitor immunotherapy (pembrolizumab) per standard of care, and eligible to undergo radiation to at least one site of disease with at least one additional site of disease that is measurable per RECIST criteria. Patient may receive radiation to asymptomatic sites of disease.
Study Product, Dose, Route, Regimen	All treatments are approved standard of care for patients with advanced urothelial carcinoma, including pembrolizumab and neutron radiation to a metastatic site. Dosing of pembrolizumab will be in accordance with their FDA label. Neutron radiation will be administered at a palliative dose/fractionation regimen to a site of disease that is either symptomatic, likely to become symptomatic, or likely to cause minimal toxicity with radiation treatment.

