Duration of administration	Checkpoint inhibitor immunotherapy will be given per standard clinical care until patients develop progression or intolerable toxicity. Neutron radiation treatments will be given standard of care as well, for a maximum of 5 daily radiation treatments.
Statistical Methodology	Overall response rate will be calculated as the percentage of patients achieving a PR or CR, and will be presented along with the 95% CI. Historical data suggest a response rate of 20%, and we hypothesize a true response rate of 40% with the proposed treatment. With 20 patients, we'll have 80% power to observe an estimated response rate that is statistically significantly higher (at the one-sided significance level of .05) than the fixed rate of 20%.

Table of Contents

1. Introduction
2. Study Objectives
3. Study Design
 - 3.1. General Design
 - 3.2. Statistical Plan
 - 3.3. Eligibility
4. Study Registration
5. Radiation Therapy
 - 5.1. Dose Specifications
 - 5.2. Localization, simulation and immobilization
 - 5.3. Target Volumes
 - 5.4. Critical Structures
 - 5.5. Treatment Planning
 - 5.6. Radiation Quality Assurance Reviews
 - 5.7. Radiation Toxicity
 - 5.8. Criteria for Removal/Withdrawal from Treatment
6. Systemic Therapy
7. Adverse Event Reporting Requirements
8. Data and Safety Monitoring Plan
 - 8.1. Early Stopping Rules
 - 8.2. Interim Data Review
9. Data Management/Confidentiality

1 Introduction

This document is a protocol for a human research study. This study is to be conducted according to US and international standards of Good Clinical Practice (FDA Title 21 part 312 and International Conference on Harmonization guidelines), applicable government regulations and Institutional research policies and procedures.

Bladder cancer has seen success with immunotherapy, although life expectancy with metastatic bladder cancer remains poor:

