3.2. Statistical Plan

This is a single-arm phase 2 study with the primary endpoint of overall response rate per iRECIST. Overall response rate will be calculated as the percentage of patients achieving a PR or CR, and will be presented along with the 95% CI. Historical data suggest a response rate of 20%, and we hypothesize a true response rate of 40% with the proposed treatment. With 20 patients, we'll have 80% power to observe an estimated response rate that is statistically significantly higher (at the one-sided significance level of .05) than the fixed rate of 20%. Secondary endpoints overall and progression-free survival will be estimated using the method of Kaplan and Meier with 95% CI obtained using Greenwood estimates of variance. Toxicities as assessed by CTCAE version 4.0 will be summarized as the proportion of patients with such toxicities, in addition to total number of toxicities (allowing for multiple toxicities within a patient) among all patients. The exploratory endpoints, change in peripheral blood cell populations will be assessed by estimating the average change between pre- and post-treatment, and these differences will be calculated for each time point; the one-sample t-test will be used to test the null hypothesis that the change is equal to zero. Trends for changes in differences from pre-treatment to post-treatment across time will be assessed using generalized linear models. Similar methods will be used to assess change in tumor biopsies for patients who consent to such analyses, where changes from pre- to post-treatment will be examined for cell death, tumor-infiltrating lymphocytes and expression of various cell-surface markers.

Should this regimen be deemed to be potentially efficacious as defined above, consideration will be given to conduct a subsequent randomized study designed to compare neutron radiation plus checkpoint inhibitors versus checkpoint inhibitors alone.

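### The stated 80% power is not delivered by 20 patients: the exact one-sided 5% test needs 8 responders and has about 58% power at a true response rate of 40%

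*Combined protocol and SAP*

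**What the plan says.** The primary endpoint is the overall response rate per iRECIST. The Study Summary sets the size of the trial at "20 evaluable subjects". Section 3.2, which the Statistical Methodology row of the Study Summary repeats, takes 20% as the historical rate, and for the alternative says "we hypothesize a true response rate of 40% with the proposed treatment". It then claims "80% power to observe an estimated response rate that is statistically significantly higher" than 20%, "at the one-sided significance level of .05".

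The estimate itself "will be presented along with the 95% CI". Section 3.2 closes with the route to a randomised trial: "Should this regimen be deemed to be potentially efficacious as defined above".

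The documents do not say whether the test is exact or approximate, how many responders count as success, or how the 95% interval is calculated. They give the interval no part in the decision.

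**The concern.** With 20 patients, a null of 20% and an alternative of 40%, 80% power at one-sided 5% looks too high for a binomial endpoint. The power figure is the only justification given for the sample size. It also determines how a negative result will be read: a reader who believes 80% will take a non-significant result as fairly strong evidence against a 40% response rate, and the decision on a randomised trial rests on that reading.

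Because no responder count is given, nobody can check the power claim against a rule. It is also left open whether 7 or 8 responders is enough, since this depends on a test that is not named. The interval adds a smaller uncertainty. A conventional two-sided 95% interval has a lower limit at the one-sided 2.5% level, so it need not agree with a one-sided 5% test at the boundary.

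**Working it through.** **Inputs**, all from section 3.2 and the Study Summary: n = 20, p0 = 0.20, p1 = 0.40, one-sided alpha = 0.05, stated power 80%. The choice of test is an assumption, so several were tried.

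**1. Exact binomial test.** Find the smallest r with P(X ≥ r | 20, 0.20) ≤ 0.05. Power is then P(X ≥ r | 20, 0.40).

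| Success if at least | Type I error at 20% | Power at 40% |
|---|---|---|
| 6/20 | 19.6% | 87.4% |
| 7/20 | 8.7% | 75.0% |
| 8/20 | 3.2% | 58.4% |
| 9/20 | 1.0% | 40.4% |

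The exact cut-off is 8/20. The chance of missing a true 40% rate is 100% − 58.4% = 41.6%, about twice the stated 20%. No cut-off gives 80% power with type I error at or below 5%: the first to exceed 80% is 6/20, with a type I error of 19.6%.

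**2. Can an approximation give the plan's 80%?**

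- Score test, with null variance for the cut-off and alternative variance for power. Cut-off: 0.20 + 1.645 × √(0.20 × 0.80/20) = 0.20 + 1.645 × 0.0894 = 0.347. Power: Φ[(0.40 − 0.347)/√(0.40 × 0.60/20)] = Φ(0.053/0.1095), which is 68.5% without rounding.
- Null variance throughout: Φ(0.20/0.0894 − 1.645) = Φ(0.591) = 72.3%.
- Alternative variance throughout (Wald): Φ(0.20/0.1095 − 1.645) = Φ(0.181) = 57.2%.
- Arcsine: 63.0%. Continuity-corrected: 60.0%.

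None reaches 80%. The uncorrected score test applied to whole counts rejects from 7/20 (nominal p = 0.047). Its true power is then the 75.0% in the table, with a true type I error of 8.7%.

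**3. What would give 80%?**

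- By the score formula: n = [(1.645 × √0.16 + 0.842 × √0.24)/0.20]² = 28.6, so 29 patients.
- By the exact test, the smallest n with at least 80% power is 35, with success at 12/35 (type I error 3.4%, power 80.5%).
- With n fixed at 20 and the 8/20 rule, power reaches 80% only at a true rate of about 47% (80.2%).

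**4. The interval beside the test.** The exact one-sided p-value at 8/20 is 0.032, which lies between 0.025 and 0.05. Clopper-Pearson limits solve P(X ≥ 8 | L) = P(X ≤ 8 | U) = α/2.

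- 95% interval: 19.1% to 63.9%, which includes 20%.
- 90% interval: 21.7% to 60.6%, which excludes 20%, as the test does.
- At 7/20 the exact p is 0.087 and the 90% interval is 17.7% to 55.8%. Both fail to reject.

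Other 95% intervals at 8/20 differ. Wald (lower limit 18.5%) includes 20%, and so does Wilson with continuity correction (19.98%). Wilson (21.9%), Agresti-Coull (21.8%), logit (21.4%), Jeffreys (21.1%), inversion of the two-sided exact test (20.9%) and mid-P (20.6%) all exclude it. From 9/20 upwards every method tried excludes 20%.

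Under the exact pairing the disagreement touches one outcome only. Its probability is 58.4% − 40.4% = 18.0% if the true rate is 40%, and 3.2% − 1.0% = 2.2% if it is 20%.

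**The case against.** The strongest reply on power is that the plan names no test, so an exact calculation cannot be held against it. That explains why there is no single right figure, but it does not rescue 80%. Every one-sided 5% method tried falls short, and the most favourable whole-count rule, 7/20, reaches 75.0% only by letting the true type I error rise to 8.7%.

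On the interval, a reader might infer something stronger: that the plan contradicts itself, that a result of 8/20 would necessarily be reported with an interval containing 20%, or that power drops to 40.4% because the interval might be used to decide. The documents do not support this. Section 3.2 only presents the interval, and it uses 95% intervals for overall and progression-free survival too, so 95% is simply its reporting level. The reference to efficacy as defined above can only mean the one-sided test, because no other criterion precedes it. The 9/20 rule behind the 40.4% appears nowhere in the plan. Whether the interval includes 20% at 8/20 depends on a method the plan does not name, and several standard methods exclude it. With an uncorrected score test and Wilson interval the disagreement moves to 7/20 (95% lower limit 18.1%). With mid-P used for both it disappears.

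That reply stands. A one-sided 5% test beside a descriptive 95% interval is acceptable practice, and moving to a 90% interval is a reporting preference.

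**Conclusion.** The power statement is wrong in both places where it appears. Under the exact one-sided binomial test, success needs 8 of 20 responders, the type I error is 3.2%, and power at 40% is 58.4%, about 22 percentage points below the stated 80%. Normal approximations give at most about 72%. This rests on the plan's own rates, alpha and sample size, with all 20 patients counted in the denominator. The 8/20 cut-off is derived here; the documents do not state one.

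The interval is a secondary, conditional point. If exact methods are used for both, the test and the two-sided 95% interval disagree at exactly 8/20. That count is the hypothesised 40% itself, so it deserves a sentence, but the test settles the decision and the design is unaffected.

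**What to change.** In section 3.2 and in the Statistical Methodology row of the Study Summary:

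1. State the success rule: at least 8 responders among 20 evaluable patients, by the exact one-sided binomial test of 20% at the 5% level (actual type I error 3.2%).
2. Replace the 80% with about 58% power at a true rate of 40%. It would help to add that 80% power is reached at a true rate of about 47%.
3. Name the interval method, and say that the test decides and the 95% interval is descriptive. If an interval that mirrors the test is wanted, add the exact two-sided 90% interval.

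These are wording changes in two places; the cost is a less favourable power figure. Keeping 80% power instead would be a change of design: about 35 evaluable patients by the exact test, 15 more than planned.

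### Twenty patients do not give the stated 80% power for 40% against 20% at one-sided 0.05: a test that holds alpha has 58%

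*Combined protocol and SAP*

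**What the plan says.** Section 3.2 describes the design as follows: "This is a single-arm phase 2 study with the primary endpoint of overall response rate per iRECIST". It then gives every input to the power calculation:

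- Null rate: "Historical data suggest a response rate of 20"%.
- Alternative: "we hypothesize a true response rate of 40% with the proposed treatment".
- Level and comparator: "at the one-sided significance level of .05) than the fixed rate of 20"%.
- Power: 20 patients will "have 80% power to observe an estimated response rate that is statistically significantly higher (at the one-sided significance level of .05").

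The Statistical Methodology entry of the Study Summary repeats the power statement, and the Number of Subjects entry gives "20 evaluable subjects". The 20 is therefore already net of dropout. Section 3.2 plans to report the response rate with a 95% CI. It does not name the test, the critical number of responders, or the formula or software behind the 80%. It closes by making a later randomized study conditional: "Should this regimen be deemed to be potentially efficacious as defined above".

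**The concern.** The power figure is the only numerical justification for enrolling 20 patients, and it concerns the primary endpoint. A comparison of 40% with 20% in 20 patients at one-sided 0.05 looks too small for 80% power. If the true power is well below that, a disappointing result could be read as evidence that neutron radiation adds nothing, when the trial had a large chance of missing the effect it was designed to find. The missing test and cutoff add to this, because methods disagree on whether 7 responders out of 20 is significant. The criterion for considering a randomized study could then turn on a choice made after the data are seen.

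**Working it through.** **Inputs.** n = 20, p0 = 0.20, p1 = 0.40, one-sided alpha 0.05 and stated power 0.80, all from Section 3.2. The Study Summary confirms that 20 is the evaluable number. The design has one stage. The interim reports in Section 8.2 list accrual, adverse events and treatment compliance, with no efficacy look.

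**Step 1: exact operating characteristics.** For the rule that rejects when X ≥ r, with X ~ Binomial(20, p), alpha = P(X ≥ r | 0.20) and power = P(X ≥ r | 0.40).

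| Reject if | True alpha | Power at 40% |
|---|---|---|
| ≥6/20 | 0.196 | 0.874 |
| ≥7/20 | 0.087 | 0.750 |
| ≥8/20 | 0.032 | 0.584 |
| ≥9/20 | 0.010 | 0.404 |

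No row combines alpha ≤ 0.05 with power of 0.80. The smallest cutoff that holds alpha is 8.

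**Step 2: does another test help?** The question is which tests reject at 7/20 = 0.35, where the critical z is 1.645.

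- Exact: p = 0.0867, no.
- Mid-p: p = 0.0594, no.
- Continuity-corrected z: (0.35 − 0.20 − 0.025)/√(0.16/20) = 1.40, no.
- Wald z: 0.15/√(0.35 × 0.65/20) = 1.41, no.
- Arcsine z: 1.52, no.
- Likelihood-ratio z: 1.56, no.
- Uncorrected z with null SE: 0.15/√(0.16/20) = 1.68, yes.

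The first six all first reject at 8/20, so all have 58.4% power. The last has 75.0% power and a true alpha of 0.087.

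**Step 3: upper bound.** By Neyman–Pearson, the most powerful test of exact size 0.05 rejects at ≥8 and randomizes at 7 with probability (0.05 − 0.0321)/(0.0867 − 0.0321) = 0.327. Its power is 0.5841 + 0.327 × (0.7500 − 0.5841) = 0.638. No test of true level 0.05 can do better.

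**Step 4: attempts to reproduce 80% with planning formulas.** Let s0 = √(0.16/20) = 0.0894, s1 = √(0.24/20) = 0.1095 and d = 0.20.

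- Null and alternative variance: Φ((0.20 − 1.645 × 0.0894)/0.1095) = 68.5%.
- The same with continuity correction (d − 0.025): 60.0%.
- Null variance only: Φ(0.20/0.0894 − 1.645) = 72.3%.
- Alternative variance only: Φ(0.20/0.1095 − 1.645) = 57.2%.
- Arcsine: 63.0%.

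The stated 80% is not reproduced. The nearest formula is almost 8 points short.

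**Step 5: what would give 80%?**

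- Keeping 20 patients and the ≥8 cutoff, P(X ≥ 8 | p) = 0.80 at p = 0.469.
- The normal approximation gives n = ((1.645 × 0.4 + 0.842 × √0.24)/0.20)² = 28.6, so 29. The exact test at n = 29 (≥10/29) has alpha 0.0493 and power 0.785.
- The smallest n at which the exact test meets both targets is 35 (≥12/35: alpha 0.034, power 0.805).

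**The case against.** The arithmetic is hard to dispute, so the case on the other side is about weight and origin.

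First, under an exact test the type I error is not raised. The response rate will be reported with a CI, and success leads only to considering a randomized study. That is fair: the harm is confined to the sample-size justification and to how a result is read. But the 80% is the only support offered for 20 patients.

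Second, Section 3.2 does give a verbal success criterion, namely significance against 20% at the stated level, so its closing reference back to a definition does point to something. That also stands. What is missing is the test and the responder count needed to apply the criterion, and at 7/20 these decide the outcome.

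Third, the slip may lie in alpha. At one-sided 0.10 the normal approximation gives 78.2% (null and alternative variance) or 83.0% (null variance only), close to 80%. This is conjecture about the source. The plan states 0.05 in both places, and at 0.10 the exact power is still 75.0%.

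Fourth, what a negative result would lead to is not in the documents. The risk of over-reading one is a possibility, not a certainty.

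**Conclusion.** The concern holds. With the plan's own inputs, power at a true 40% is 58.4% for any of the six tests that first reject at 8/20 (true alpha 0.032). It is 75.0% for the uncorrected z-test, which breaches the stated level with a true alpha of 0.087. Type II error is 41.6% or 25.0%, against the 20% implied. The shortfall is about 22 points for a non-randomized test that holds alpha, and 5 points in the most favourable case, so rounding or choice of formula does not explain it. This rests on 20 evaluable patients with independent responses, a single final analysis and a null fixed at 20%, all as the plan has them.

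**What to change.** Name the test and the cutoff, and restate the power, in both Section 3.2 and the Statistical Methodology entry of the Study Summary. Wording that keeps 20 patients:

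> The null response rate of 20% will be tested with a one-sided exact binomial test and rejected if at least 8 of 20 evaluable patients respond (actual alpha 0.032). Power is 58% at a true rate of 40% and 80% at a true rate of about 47%.

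This costs only wording and no extra patients, but the stated power becomes less favourable. The sponsor has two other routes:

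- **Relax alpha openly:** reject at ≥7/20, with nominal alpha restated as 0.10 (actual 0.087) and power as 75%.
- **Keep 0.05 and 80% at a true 40%:** enrol 35 evaluable patients, 15 more than planned, rejecting at ≥12/35. Exact power is not monotone in n (it falls to 0.778 at n = 37), so any other size needs its own check.

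As an optional addition, name the CI method. A two-sided 95% interval corresponds to a one-sided 0.025 test, so at 8/20 the Clopper–Pearson lower limit is 19.1% even though the test rejects. An exact 90% interval (21.7% to 60.6%) would match the test. The plan does not use the interval to decide success, so this is not a contradiction.

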Although classical radiation biology states that the cytotoxic effects of radiation on tumor cells are primarily initiated by DNA double strand breaks, there is an emerging understanding of the importance of an “immunogenic cell death” (ICD) as a significant *in vivo* cell death mode. Radiation has been shown to induce all 3 key components of ICD: cell surface translocation of calreticulin to signal dendritic cells, and release of danger signals such as HMGB1 and ATP, which result in priming of CD8+ T-cells²¹. Tumor mutational burden and defects in the DNA repair pathway have been linked to tumor response rate to checkpoint inhibitors such as anti-PD-1 therapy. While bladder cancer is the third highest mutated cancer²², high RBE particle therapy such as neutrons cause qualitative changes in the sub-cellular distribution and types of DNA damage, and have the potential to shift cells from an apoptotic cell death mode towards the more inflammatory, and possibly immunogenic, mitotic catastrophe and necrotic cell death modes.²³⁻²⁵ High RBE therapy may cause a more immunogenic tumor microenvironment via release of more tumor neoantigens^{26,27}. Mouse total body radiation experiments in the 1970s with neutrons versus standard photons found that the degree of immunosuppression was dependent on the LET of the radiation (neutrons have high LET), and mortality from total body radiation differs based on LET, for the same delivered radiation dose²⁸.

Immunologic changes in peripheral blood of patients receiving immunotherapy:

Immune profiling of peripheral blood from patients on checkpoint inhibitor immunotherapy has not been widely explored. Huang *et al.* looked at peripheral blood of 29 patients with metastatic melanoma receiving anti-PD-1 antibody pembrolizumab²⁹. At 3-weeks into therapy, frequency of Ki67+ CD8 T-cells peaked and then declined, with highest percent of Ki67+ CD8 T-cells around weeks 3-6 after start of pembrolizumab (Ki67+ CD8 T-cells increased from around 7% at baseline to around 14-19% at weeks 3-6 post-pembrolizumab). The increase in Ki67 expression was mostly seen in the PD-1+ versus PD-1 negative CD8 T-cells, with Ki67 increasing from around 9% at baseline to around 23% at 3-weeks (peak response) in the PD-1+ CD8 T-cells population, and non-statistically significant increase in Ki67+ cells in the PD-1 negative CD8 T-cell population (Figure 1). Clinical response was correlated with the fold change of PD-1+ Ki67+ CD8 T-cells after

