3.1 General Design

This is a study to test whether densely ionizing, high relative biologic equivalence (RBE) radiation in the form of neutron radiation, can improve the response rate to checkpoint inhibitor immunotherapy in patients with advanced urothelial carcinoma. In this trial, the addition of focal radiation is hypothesized to act as a “vaccine” by releasing tumor neoantigens, with the goal being to augment the immune response. Trial schema is shown below in Figure 1 and study calendar in Table 1. Patients with advanced urothelial carcinoma about to receive checkpoint inhibitor therapy (pembrolizumab), with at least two sites of measurable disease per RECIST 1.1, will undergo neutron radiation to 1-3 sites of disease. At least one site of RECIST 1.1 evaluable disease must remain untreated³¹, as only non-radiated sites will serve as index lesions to assess for response rate per iRECIST criteria.³⁰ Asymptomatic lesions are eligible for radiation as the primary goal of the radiation therapy is to induce an immune response.

[figure not shown]

Figure 2. Clinical trial schema.

Table 1. Study Calendar.

	Pre-treatment⁴	Between Dose 2 and 3 of Immunotherapy⁵	4-Weeks After End of Radiation⁶	16-Weeks After End of Radiation⁷
Informed Consent	X			
Medical History	X		X	X
Physical Exam	X		X	X
ECOG Performance Status	X		X	X
Blood Draw¹	X	X	X	X
Radiation Therapy		X		
Tumor biopsy (optional)²		X		X
CT C/A/P³	X		X	X

¹Blood draw will consist of 9 tubes: 8 yellow top tubes (BD Vacutainer #364606 Acid citrate dextrose additives ACD Solution A) and 1 red top tube (BD Vacutainer #367820 Clot Activator) to collect and store the following: 1) 6 tubes of 0.5 ml serum; 2) 2 tubes of 1.0 ml plasma; 3) 4 tubes of 0.5 ml PBMC; and 4) 6 tubes of 1 ml PMBC.

²Tumor biopsy of a radiated or non-radiated site will be performed for patients who consent.

³CT C/A/P is preferred but MRI or PET/CT also acceptable.

⁴All pre-treatment assessments must be performed within 30 days of protocol enrollment, except CT C/A/P which must be within 45 days of protocol enrollment.

Pembrolizumab is typically given every 3 weeks. Dose 2 must happen between 2.5-5 weeks after dose 1, and dose 3 must happen between 6-9 weeks after dose 1.

⁶Acceptable date range is 3 to 6 weeks after radiation ends.

⁷Acceptable date range is 12 to 24 weeks after radiation ends.

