Time points for peripheral blood collection are based on prior studies, including Huang *et al.* and Twyman-Saint Victor *et al.* described above^{9,29}, that show peak changes in peripheral blood immune cell populations around 3-6 weeks post start of therapy for checkpoint inhibitor immunotherapy, and changes after radiation treatment that peak around 2-4 weeks but can persist for months after treatment.

After the study period as outlined above, all patients will be followed at least once every 3 months by the treating oncologist per standard of care. Toxicity, disease response, and survival will be recorded at each clinic visit. Patients are considered off-study once disease progression is detected per iRECIST³⁰. Follow up with radiation oncology is not required but records will be obtained from treating oncologist. All correlative studies will be batched for analysis.

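### The trend analysis of the blood markers names generalized linear models but does not say how up to three changes per patient from one baseline draw are handled, so its standard error is generally wrong, in a direction the documents do not fix

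*Combined protocol and SAP*

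**What the plan says.** Section 3.2 (Statistical Plan) sets out two analyses of the peripheral blood cell populations. In the first, changes from pre-treatment are averaged, "these differences will be calculated for each time point", and "the one-sample t-test will be used to test the null hypothesis that the change is equal to zero". The second concerns the course over time: "Trends for changes in differences from pre-treatment to post-treatment across time will be assessed using generalized linear models". That sentence is the whole specification of the trend analysis. It gives no link function, time coding, working correlation, random effect or variance estimator.

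Table 1 in section 3.1 schedules four blood draws: pre-treatment, "Between Dose 2 and 3 of Immunotherapy", 4 weeks after radiation (window 3 to 6 weeks) and 16 weeks after radiation (window 12 to 24 weeks). The study summary plans 20 evaluable subjects. Section 3.1 also says: "Patients are considered off-study once disease progression is detected per iRECIST". It does not say whether blood draws stop at that point.

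**The concern.** Each patient can contribute three changes, all formed by subtracting the same pre-treatment value. They are correlated through that value, and further correlated if patients differ in how strongly they react. A generalized linear model, as the term stands, treats its rows as independent.

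The effect on the trend is not the familiar one, in which ignored clustering makes standard errors too small. A slope over time is mainly a within-patient contrast, so positive correlation usually makes its true standard error smaller than the independence formula reports. The opposite can happen when patients drift apart over time, or when late draws are missing and the slope becomes partly a comparison between patients.

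This model is the only planned test of whether marker changes grow or fade across draws. With a wrong standard error, it may lose power or overstate a trend.

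**Working it through.** The plan gives no figure for this analysis, so there is none to reproduce.

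**Inputs from the documents.** 20 patients; three post-baseline draws per patient; one shared baseline; 20 × 3 = 60 values at most.

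**Assumptions.** Draws at weeks 5, 10 and 22; two-sided 5% test; the named model fitted as ordinary least squares on all rows. The change for patient i at draw j is b_i f(t_j) + e_ij − e_i0, with Var(e) = 0.5. One change then has noise SD 1, and two changes correlate 0.5 through the baseline alone. The patient effect b_i has mean 0 and SD q (1 to 3 times the noise SD), and f sets how patients spread over time.

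**Standard error with complete draws.** Let V be the 3 × 3 covariance of one patient's changes and d = (−7.33, −2.33, 9.67) the centred times, so S = Σd² = 152.67.

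- True slope variance: τ/(20S), with τ = d′Vd/S.
- Variance the model reports, on average: E[s²]/(20S), with E[s²] = (20 tr V − 1′V1/3 − τ)/58.
- Ratio of reported to true SE: √(E[s²]/τ).

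Three cases:

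- Common slope (q = 0): tr V = 3, 1′V1 = 6, τ = 0.5. E[s²] = (60 − 2 − 0.5)/58 = 0.991. Ratio √(0.991/0.5) = 1.41.
- Persistent patient differences, f = 1/1/1, q = 1: tr V = 6, 1′V1 = 15, τ = 0.5. E[s²] = (120 − 5 − 0.5)/58 = 1.974. Ratio 1.99.
- Late divergence, f = (t − 5)/17, q = 3: d′f = 8.98, τ = 0.5 + 9 × 8.98²/152.67 = 5.25, tr V = 12.78, 1′V1 = 21.07. E[s²] = (255.6 − 7.0 − 5.25)/58 = 4.20. Ratio √(4.20/5.25) = 0.89.

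**Type I error of the model as named.** Simulation, 20,000 trials per setting, in %, for q = 1/2/3. The missing-draw column assumes 40% of 16-week and 13% of 4-week draws lost at random.

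| How patients differ over time | Complete | Draws missing |
|---|---|---|
| Common slope (q = 0) | 0.8 | 1.5 |
| Early, then fading (1/.8/.2) | 1.1/1.5/1.8 | 1.0/0.6/0.6 |
| Peak at 4-week draw (.5/1/.5) | 0.2/0.0/0.0 | 0.6/0.1/0.0 |
| Fading to zero (1/.5/0) | 2.2/4.6/5.7 | 1.9/2.4/2.6 |
| Persistent (1/1/1) | 0.0/0.0/0.0 | 0.5/0.2/0.1 |
| Diverging from dose 1 (t/22) | 1.3/2.1/2.4 | 3.8/7.2/9.2 |
| Late divergence ((t − 5)/17) | 2.7/6.4/8.2 | 5.4/12.4/16.3 |

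**Power, complete draws.** With the slope set so that a patient-clustered test has 80% power, the model as named has 56% (common slope), 60 to 66% (early then fading), 72% (fading to zero, q = 1), 36% (peak at 4-week draw, q = 1) and 20% (persistent, q = 1).

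**Dependence on missing draws.** A wider grid of 34 covariance and time-coding settings was run at three levels of loss. Counts are of SEs more than 2% off.

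| Conditional loss before draws 2 and 3 | SE too large | SE too small | Range of ratio |
|---|---|---|---|
| None | 30 | 4 | 0.84 to 1.41 |
| 15% and 30% | 20 | 12 | 0.65 to 1.26 |
| 30% and 50% | 12 | 17 | 0.51 to 1.16 |

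**Check of the remedy.** The same slope with a patient-clustered variance, G/(G − 1) correction (G = number of patients) and t with 19 degrees of freedom gives about 4.4 to 5.2% with complete draws. With 20% or 40% of 16-week draws missing it gives about 2.8 to 6.3%. With 30% and 65% of draws missing it rises to 7.7 to 10.2% under the divergence shapes, so the small-sample correction should be named.

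**The case against.** The strongest reply is that a one-sentence exploratory plan may use the term loosely, with GEE or a mixed model in mind. That is possible. The text does not say so, and different readings of it can give different conclusions from the same data. If GEE was meant, the edit records it.

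A second reply is that every magnitude here rests on assumed SDs, draw times and missing rates. That stands for the sizes and the direction. It does not touch the absence of any provision for repeated draws. Nor is the error universal under the independence fit: when patient differences fade to zero and q is 2 or 3, type I error with complete draws is 4.6 to 5.7%, close to nominal.

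Two stronger readings are tempting. A reader might infer that the test would most likely miss real trends. The figures do not support that in general: in several shapes it keeps 56 to 72% power, and only the persistent and 4-week-peak cases fall below half.

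A reader might also infer that the direction is known, because the Introduction reports that the "frequency of Ki67+ CD8 T-cells peaked and then declined" and section 3.1 cites "changes after radiation treatment that peak around 2-4 weeks but can persist for months after treatment". Those statements describe how markers move over time. They do not say how the spread between patients changes, and that spread is what drives the direction.

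**Conclusion.** The point holds as a gap in the specification with a real consequence. If the sentence is followed as written, up to 60 correlated values are analysed as independent and the trend standard error is generally wrong. With complete draws it is too large in most assumed settings, and the test loses power. Under divergence between patients, particularly with late draws missing, it can be too small, with type I error up to about 16% in the scenarios tried. Which applies cannot be determined from the documents.

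A reader might also infer that the shared baseline biases the slope. With all three draws present the baseline value cancels from a patient's slope; the fault lies in the standard error.

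The stakes are limited. The endpoints are exploratory and the plan attaches no decision rule to them. The per-time-point t-tests use one value per patient and are sound in this respect, and the response-rate analysis is untouched. This is a change worth considering, not an obstacle to the trial.

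**What to change.** Replace the trend sentence in section 3.2 with:

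*Trends across post-treatment draws will be estimated using actual draw time with GEE or linear regression with patient-clustered variance, a named small-sample correction (for example CR2 or Mancl-DeRouen) and a t reference based on the number of patients; a mixed model with patient random effects will be a sensitivity analysis.*

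Actual draw time matters because the last window spans 12 to 24 weeks after radiation. The simulations above used the simpler G/(G − 1) correction; CR2 and Mancl-DeRouen were not simulated.

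The plan should add that this corrects the standard error but not bias from draws lost for reasons related to the marker, such as loss around progression, and should report the number of draws available at each visit. The cost is a short text edit, with no added samples, visits or patients.
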